#### 6.2.3 Tumor Markers

Tumor markers alone cannot be used to assess response.

#### 6.2.4 Clinical Examination

Clinically detected lesions will only be considered measurable when they are superficial (e.g., skin nodules and palpable lymph nodes). For skin lesions, documentation by color photography, including a ruler to estimate size of the lesion, is recommended. Photographs should be retained at the institution.

#### 6.2.5 Cytology and Histology

Cytologic confirmation of the neoplastic nature of any effusion that appears or worsens during treatment is required when the measurable tumor has met response or stable disease criteria.

#### 6.2.6 Ultrasound

Ultrasound may be used only as an alternative to clinical measurements for superficial palpable lymph nodes, subcutaneous lesions, and thyroid nodules.

Rev. 6/14  
Rev. 2/15  
  
Rev. 1/16  
Rev. Add8

## 7. Study Parameters

### 7.1 Therapeutic Parameters

1. Prestudy scans and x-rays used to assess all measurable or non-measurable sites of disease must be done within 30 days prior to randomization/registration.
2. Prestudy CBC (with differential and platelet count) should be done ≤ 4 weeks before randomization/ registration.
3. All required prestudy chemistries, as outlined in Section 3, should be done ≤ 4 weeks before randomization/registration – unless specifically required on Day 1 as per protocol.

**Table 3.**

Rev. 2/14.  
Rev. 9/16  
Rev. Add8

	Prior to Registration/Randomization	Day of Surgery	First Post-operative week	4-6 Weeks After TORS	At completion of treatment (Arms B, C, D), observation (Arm A), or Arm S patients who do not register to Step 2	LTFU Arms B, C, D Observation (Arm A), or Arm S patients who do not register to Step 2
Medical history, PE, Vital signs	X	X	X		X	X 
Height	X					
Weight	X	X	X	X	X	X 
ECOG Performance status	X	X	X	X	X	X 
CBC w/diff, plts	X	X 	X		X	X 
Serum chemistry	X	X 	X		X	X 
Adverse event evaluation	X		X		X	X 
Disease Evaluation by clinical methods 	X					X
Tumor tissue	X					
CT SCAN with contrast/MRI of neck 	X					X
B-HCG	X					
Dental evaluation 	X					
Nutrition consult 	X					
SLP consult with MBS 	X			X		X 
Feeding tube placement			optional			
Patient Reported Outcomes	See Appendix V					
Biological specimen submissions	See Section 7.2					

Rev. 2/14,  
6/15  
  
Rev. 2/14,  
Rev. 2/15

1. 6 months and 24 months after treatment. These are required for sites participating in the MBS sub-study (See [Appendix V](#)). Results of these tests are also requested from sites that perform these as standard of care. Videos should be uploaded to the cloud at MD Anderson Cancer Center.
2. Arms B, C, D assessments will be done at 10-12 weeks after completion of treatment, Arm A will be done 17-19 weeks from registration to step 2, and Arm S will be done 23-25 weeks following surgery; then every 3 months for the first 2 years, every 6 months for the third year, and every 12 months for the fourth and fifth year or until progression.

Rev. 2/14  
Rev. 6/14  
Rev. 2/15  
Rev. 9/16

3. Disease evaluation by clinical methods and a CT and/or MRI will be obtained at baseline ( $\leq 30$  days before registration), 10 - 12 weeks after completion of treatment [Arms B, C, D] or 17-19 weeks from registration to step 2 [Arm A] or 23 -25 weeks following surgery [Arm S]; then every 6 months for the first 3 years, and every 12 months for the fourth and fifth year, or until progression.
4. For sites participating in the MBS substudy, MBS videos completed by the site will be stripped of patient identifiers, renamed with an EA-designated ID number, and uploaded to the Box® Cloud-based storage account maintained by MD Anderson Cancer Center. EA-designated ID number is obtained via the ECOG-ACRIN Sample Tracking System. Follow the instructions for the submission of these outlined in Section 10.1.6.
5. All labs may be completed within 7 days of surgery.
6. Dental status and nutritional status (weight loss) must be evaluated and documented by the surgeon prior to the day of surgery. A referral and consultation with a specialist may be needed prior to surgery if abnormalities are noted.

## 7.2 Biological Sample Submissions

Samples are to be submitted as outlined in Section [11](#). Submission requirements are indicated by Treatment Arm in the table below.

**NOTE:** All samples submitted must be logged and tracked in the ECOG-ACRIN Sample Tracking System (STS).

Rev. 6/14,  
2/15

	Baseline	Within 4 wks post-surgery	Step 2, Week 4 	Step 2, End of trt	Step 2, 1 st RTC appointment after EOT (~12 weeks)	q 3mon  x 2 yrs	q 6mon  x 2 yrs
MANDATORY: Submission of these materials are REQUIRED to determine patient evaluability and for surgical quality assurance review.							
Diagnostic p16 Tumor Slide	S 						
Pathology and Surgical Reports	S 	S 					
Per patient consent: Submit from patients who have answered "Yes" to " I agree to provide additional specimens for research. "							
Serum, from 1 x 10 mL Red-top no anti-coagulant 	S	S	B,C,D	B,C,D	B,C,D		A,B,C,D, S
Peripheral Blood lymphocytes and plasma, 4 x 10mL EDTA vacuainer 	S	S	B,C,D	B,C,D	B,C,D		A,B,C,D, S
Oral rinse 	S	S		B,C,D		A,B,C,D,S	
Tumor Tissue, Fixed and Frozen 		S					

- Rev. 6/14 1. The requested pathology materials and reports are to be submitted as outlined in Section [11](#) upon finalization of the surgical pathology report but no later than 4 weeks following the performance of the surgery.
- Rev. 2/14 2. For Arms A, B, C, and D the collection time points are from the start of Step 2 treatment. Arm S patients not registered/randomized to Step 2, collection time points are from time of surgery.
3. Collect Monday – Thursday only. Do not collect the day before a weekend or holiday. Samples are shipped the day of collection and must be processed immediately upon receipt.
- Rev. 6/14 4. Frozen Samples are to be shipped on dry ice. Original diagnostic or surgical specimens may be submitted.
5. Samples may be batched and submitted on a quarterly basis.
- Rev. 6/14 6. Samples should be collected 30 minutes prior to or 2 hours after eating to reduce potential contamination from food.

## 8. Drug Formulation and Procurement

### 8.1 Cisplatin

#### 8.1.1 Other Names

Cis-diaminedichloroplatinum Cis-diaminedichloroplatinum (II), diaminedichloroplatinum, cis-platinum, platinum, Platinol , Platinol-AQ , DDP, CDDP, DACP, NSC 119875 R R

#### 8.1.2 Classification

Alkylating agent

#### 8.1.3 Mode of Action

Inhibits DNA synthesis by forming inter- and intra-strand crosslinks. Other possible mechanisms include chelation of DNA and binding to cell membranes thereby stimulating immune mechanisms.

#### 8.1.4 Storage and Stability

Intact vials of cisplatin are stored at room temperature. Solutions diluted with saline solution are stable for up to 72 hours at room temperature. Due to the risk of precipitation, cisplatin solutions should **not** be refrigerated.

#### 8.1.5 Dose Specifics

40 mg/m^2 IV day 1, each week of radiation therapy, on Arm D only.

#### 8.1.6 Preparation

The desired dose of cisplatin is diluted with 250-1000 ml of saline solution.

Varying concentrations of 0.225-5% sodium chloride may be used. To maintain stability of cisplatin, a final sodium chloride concentration of at least 0.2% is recommended.

#### 8.1.7 Route of Administration

Cisplatin is administered as an intravenous infusion over 60 minutes.

#### 8.1.8 Incompatibilities

Amsacrine, cefepime, gallium nitrate, mesna, piperacillin, sodium bicarbonate, thiotepa. Cisplatin may react with aluminum which is found in some syringe needles or IV sets, forming a black precipitate.

#### 8.1.9 Compatibilities

Admixture: Amphotericin-B, aztreonam, carmustine, cefazolin, cephalothin, droperidol, etoposide, floxuridine, hydroxyzine, ifosphamide, leucovorin, magnesium sulfate, mannitol, potassium chloride.

Y-site: Allopurinol, bleomycin chlorpromazine, cimetidine, cyclophosphamide, dexamethasone, diphenhydramine, doxapram, doxorubicin, famotidine, filgrastim, fludarabine, fluorouracil,

furosemide, ganciclovir, heparin, hydromorphone, lorazepam, melphalan, methotrexate, methylprednisolone, metoclopramide, mitomycin, morphine, ondansetron, paclitaxel, prochlorperazine, ranitidine, sargramostim, vinblastine, vincristine, vinorelbine.

Consult your pharmacist regarding specific concentrations

8.1.10 Availability

Commercially available as a 1 mg/ml solution in 50 and 100mg vials. Vials of lyophilized powder are no longer commercially available, but may be obtained directly from the manufacturer for chemoembolization use.

8.1.11 Side Effects

1. Renal: A dose-related, cumulative renal tubular injury can occur; adequate hydration and diuresis usually minimize the risk. Salt-wasting nephropathy and/or orthostatic hypotension with hyporeninemic hypoaldosteronism can occur in up to 10% of patients.
2. Neurologic: A dose-related ototoxicity, manifested by high-frequency hearing loss and tinnitus, occurs in about 30% of patients. Paresthesias, decreased vibratory, position, and touch sensations are less common; particularly at cumulative doses <400 mg/m^2.
3. Hematologic: Mild leukopenia and thrombocytopenia occur in 25-30% of patients, but are rarely dose-limiting; anemia is less common. A potentially fatal hemolytic uremic syndrome has been reported.
4. Gastrointestinal: Severe, dose-limiting nausea and vomiting occur in almost 100% of patients unless adequate antiemetic prophylaxis is given. Even with successful prophylaxis of acute nausea a delayed (72-96 hour) reaction, requiring additional therapy may occur. Anorexia and taste changes may also occur.
5. Hypersensitivity: Allergic reactions are reported in up to 20% of patients Symptoms include: rash, facial edema, wheezing, hypotension, and tachycardia. Severe anaphylaxis is rare.
6. Other: Electrolyte wasting (magnesium, potassium and sodium), papilledema, optic neuritis, retrobulbar neuritis are reported.

8.1.12 Nursing/Patient Implications

1. Prior to administration, assess:
  - A. Labs: CBC, platelet count, BUN, creatinine.
  - B. Urine output: 100-150 ml/hr for at least 4-6 hours.
  - C. Signs of ototoxicity or neurotoxicity.
2. Administer supportive medications:
  - A. Premedicate with antiemetics – prophylaxis with a 5 – HT3 receptor antagonist and dexamethasone (+/- aprepitant) is standard.

B. Hydration

C. Diuretics - may be ordered.

3. Observe for signs of allergic reaction.

## 8.2 Carboplatin

### 8.2.1 Other Names

CBDCA, Paraplatin, JM-8, NSC-241240

### 8.2.2 Classification

Second-generation tetravalent organic platinum compound

### 8.2.3 Mode of Action

Like cisplatin, carboplatin binds to DNA, thereby inhibiting DNA synthesis, in a cell cycle nonspecific manner. Carboplatin must first undergo activation to produce antineoplastic activity. Bidentate carboxylate ligands of carboplatin are displaced by water forming (aquation) positively charged platinum complexes which bind to nucleophilic sites in DNA, such as the O-6 position on guanine. Carboplatin produces predominantly interstrand DNA crosslinks rather than DNA-protein crosslinks. Intrastrand crosslinks result from the formation of adducts between the activated platinum complexes of the drug and the N-7 atom (not exclusively) atom on guanine to produce 1,2 intrastrand links between adjacent guanine molecules, between neighboring guanine and adenosine molecules, or between

neighboring guanine molecules. Interstrand cross-linking within the DNA helix also occurs. Platinum adducts may inhibit DNA replication, transcription and ultimately cell division.

#### 8.2.4 Storage and Stability

Intact vials are stored at room temperature protected from light. The reconstituted solution is stable for at least 24 hours. When further diluted in glass or polyvinyl plastic to a concentration of 10mg/mL with normal saline or 5% dextrose carboplatin is stable for 8 hours at 25 degrees C. Stability with further dilution to 0.5mg/mL has been reported for up to 8 hours. Other stability data indicate that carboplatin is stable for up to 24 hours and may be refrigerated, however, the manufacturer recommends that reconstituted solutions be discarded after 8 hours due to the lack of preservative in drug formulation.

#### 8.2.5 Dose Specifics

Carboplatin will be given by IV at an area under the curve (AUC) dose of 2. Routine premedication should include at least a 5 – HT3 antagonist and dexamethasone. The dose of carboplatin based on target AUC is calculated using the Calvert equation:

Dose (total mg) = Target AUC X (GFR + 25). The patient's creatinine clearance (GFR) in mL/minute is calculated by the Cockcroft Gault equation.

**NOTE:** When using the Calvert equation, GFR should not exceed 125 mL/min. Thus, the maximum carboplatin dose is  $2 \times (125 + 25)$ , or 300 mg.

#### 8.2.6 Preparation

Add 5, 15, or 45 mL sterile water, normal saline, or 5% dextrose to the 50, 150, or 450 mg vial, respectively. The resulting solution contains 10 mg/mL. The desired dose is further diluted, usually in 5% dextrose.

#### 8.2.7 Administration

Infuse over 30 minutes.

#### 8.2.8 Incompatibilities

Aluminum displaces platinum from the carboplatin molecule, resulting in the formation of a black precipitate and loss of potency. Carboplatin solutions should not be prepared or administered with needles, syringes, catheters, or IV administration sets containing aluminum parts that might be in contact with the drug.

#### 8.2.9 Drug Interactions

Concomitant myelosuppressive drugs or radiation therapy may potentiate the hematologic toxicity of carboplatin.

Concomitant nephrotoxic drugs may potentiate the nephrotoxicity of carboplatin, particularly when carboplatin is given in high-dose chemotherapy regimens.

- 
- 8.2.10      Compatibilities
- Carboplatin (0.3 mg/mL) and etoposide (0.4 mg/mL) are chemically compatible in normal saline or 5% dextrose for 24 hours at room temperature.
- 8.2.11      Availability
- Commercially available as a lyophilized powder in 50, 150, or 450 mg vials.
- 8.2.12      Side Effects
1. Hematologic: Thrombocytopenia (dose limiting), neutropenia, leukopenia, anemia.
  2. GI: Nausea and vomiting (frequent but less severe than with cisplatin), treatable with appropriate antiemetic prophylaxis. Anorexia, diarrhea and constipation have also been reported.
  3. Dermatologic: Rash, urticaria. Rarer reactions include alopecia, mucositis, and hypersensitivity reactions.
  4. Hepatic: Abnormal liver function tests, usually reversible with standard doses.
  5. Neurologic: Rarely peripheral neuropathy is seen. May be more common in patients greater than 65 years of age. May also be cumulative, especially in patients with prior cisplatin treatment. Ototoxicity (rare).
  6. Renal: Elevations in serum creatinine, BUN; electrolyte loss (Mg, K, Na, Ca).
  7. Miscellaneous: Pain, asthenia, flu-like syndrome.
- 8.2.13      Nursing Implications
1. Monitor CBC and platelet count routinely.
  2. Premedicate with antiemetics – prophylaxis with a 5HT3 receptor antagonist and dexamethasone (+/- aprepitant) is standard.
  3. Monitor fluid status – maintain adequate hydration.
  4. Assess skin/mucous membranes.
  5. Assess for signs of peripheral neuropathy – coordination, sensory and hearing loss.
- 8.2.14      References
1. American Hospital Formulary Service 2003-Drug Information.
  2. Calvert AH, et al. Carboplatin dosage: Prospective evaluation of a simple formula based on renal function. *J Clin Oncol* 7: 1748-56, 1989.
  3. Carboplatin package insert, Princeton, NJ; Bristol Laboratories Oncology Products 1998; June
  4. Christian MC. Carboplatin. In: *Principles and Practice of Oncology*, PPO Updates 3(11): 1-16, 1989.
-

Rev. 1/16

## 9. Statistical Considerations

Rev. 2/15

This is a phase II trial of p16+ (using immunohistochemistry (IHC)) OPSCC patients that will undergo transoral surgery (TOS, Step 1) followed by risk-adjusted radiotherapy (Step 2). Patient risk status is determined after surgical excision and is defined in Section 5.1. Patients with low-risk will be assigned to the observation group (Arm A). Patients with intermediate-risk (the primary study group) will be equally randomized to receive radiotherapy IMRT 50 Gy (Arm B) or 60 Gy (Arm C), stratified by current/former smoking history ( $\leq 10$  vs.  $> 10$  pack-years). Patients with pathological N2C/N3 disease without extensive ECS (and do not meet the high risk feature) will be directly assigned to Arm C receiving IMRT 60 Gy. Patients with high-risk will receive concurrent cisplatin and IMRT 66 Gy (Arm D). Among the first 10 patients enrolled on Arm A, if 2 or more progress or die within 1 year, currently enrolled and subsequently enrolled patients with low risk who have not progressed will be directly assigned to radiotherapy 50 Gy (details are given below).

The study requires 180 evaluable patients with intermediate risk (to be randomized between Arms B/C). Based on results from the interim analysis prepared for the Fall 2015 DSMC meeting, the overall proportion of evaluable patients with intermediate risk is estimated to be 35% (~73% patients are evaluable, among whom ~48% are intermediate risk), which is lower than the originally estimated 48% (80% evaluable, among whom 60% would be intermediate risk). Here, patients who are eligible and started treatment on step 2 are considered as evaluable. As stated in the original design, if the observed proportion of patients with intermediate risk is off over 5% from the anticipated 60%, accrual goal would be adjusted. Therefore, the current section incorporates a sample size increase from the originally proposed 377 to 515 ( $180/0.35=515$ ), to ensure 180 evaluable patients with intermediate risk to be randomized. Based on the observed accrual rate of 18.5 patients per month, this new accrual goal can be achieved in February, 2017.

### 9.1 Objectives

The primary objectives of this phase II study are: 1) to examine the **feasibility** of a prospective multi-institutional study of TOS followed by risk-adjusted adjuvant therapy in this patient population; and 2) to assess the oncologic **efficacy** of the proposed treatment strategy (TOS + reduce dose radiotherapy) for the intermediate risk group. The accrual rate, patient risk distribution (especially the proportion of the intermediate risk group), and surgical quality are used to evaluate feasibility of the study. The 2-year progression-free survival (PFS) rate will be used to evaluate the efficacy in the intermediate risk group. The table below gives a summary of the stopping rules / decision rules to be implemented with regard to these two primary objectives. Details are given in following sections.

Rev. 2/15

Objective	Endpoint	Assessment Time point	Suspension rules / Decision Rules
Efficacy	1-year PFS rate	First 10 patients in arm A followed for 1 year	Currently enrolled and subsequent patients who have not progressed will receive radiotherapy 50 Gy if 2 or more patients progress or die within 1 year
	1-year PFS rate	First 10 patients with p N2C/N3 disease followed for 1 year	Currently enrolled and subsequent patients with p N2C/N3 disease who have not progressed will receive IMRT 66 Gy + cisplatin (Arm D treatment) if 2 or more patients progress or die within 1 year
	1-year PFS rate	First 40 patients in each of arms B and C followed for 1 year	Suspend trial and review if $\geq 6$ patients (per arm) progress or die within 1 year
	2-year PFS rate	End of study	Treatment worthy of further study if higher limit of the 90% CI $> 85\%$
Feasibility	Accrual	13-18 months post-activation	Accrual will be monitored by DSMC and NCI (see section below)
	Risk distribution	First 59 patients evaluated for risk	Suspend trial and review if $\leq 21$ patients with intermediate risk
	Surgical quality	First 59 patients completed transoral resection and have CTCAE forms submitted	Suspend trial and review if $\geq 13$ patients reported with grade 3-4 bleeding or positive margins

Secondary objectives include assessing quality of life (QOL) and swallowing function before and after treatment, evaluating toxicity, and investigating the prognostic effects of various biomarkers (details follow).

## 9.2 Sample Size and Accrual Rate

We plan to accrue 515 patients, expecting ~376 (73%) total patients would be evaluable (eligible and treated on step 2), among whom 180 would be intermediate risk. Observed accrual rate (18.5 patients per month) is higher than the original assumption of 8 patients per month, so accrual of 515 patients is expected to complete in February, 2017.

## 9.3 Primary Objective: Efficacy

### *Primary Endpoint—2-year PFS rate*

The sample size calculations are based on the efficacy endpoint of 2-year PFS rate, which is defined as the proportion of patients alive and progression-free at 24 months measured from date of registration onto Step 1. Patients who die without disease progression within 24 months and patients who begin non-protocol therapy without evidence of progression within 24 months will not be considered to be progression-free at 24 months. The 2-year failure proportions that include second primary cancers from the head and neck region as event will also be reported.

The regimen of TOS + low-dose radiation (Arm B and Arm C, separately) may be considered worthy of further study if the true 2-year PFS rate is close to 85% (the observed rate among high-dose radiation patients in E2399).

Assuming 90 analyzable patients per arm for the intermediate group, the following table displays the exact 90% binomial confidence intervals (CIs) for the 2-year PFS rate for each of Arm B and C, assuming various observed 2-year

Rev. 6/14

PFS rate. For example, if 79 out of 90 analyzable patients per arm are alive and progression free at 2 years, the 90% confidence interval will be 81% to 93% with a width of 12%. This study will need 180 analyzable patients in total for the two randomized arms (Arms B + Arm C).

	Number of Alive and Progression Free at 2 Years			
	71	75	79	83
90% CI	(0.71, 0.86)	(0.76, 0.89)	(0.81, 0.93)	(0.86, 0.96)

With regard to p16 status, while central evaluation of pathology reports will be conducted retrospectively, actual assays will not be run or reviewed centrally. Patients who drop-out prior to radiation therapy due to any reason will also be excluded from the primary analysis .

In the original design, the risk distribution was assumed to be 10% low risk, 60% intermediate risk, and 30% high risk, and an interim analysis for the first 59 patients who complete transoral resection was scheduled. Based on the analysis results, among the 104 evaluable patients (not ineligible based on current evaluation, and started treatment on step 2), the estimated risk distribution is: 8% low risk, 48% intermediate risk and 32% high risk (13 (12%) patients had potentially misclassified risk category/ arm based on their surgical data and the study team is taking various actions trying to improve this). As was stated in the original design, in case the proportion of the intermediate risk patients is off over 5% from the anticipated 60%, the accrual goal would be adjusted, With this new accrual goal, we expect at the end of the study ~180 evaluable patients would be intermediate risk, ~120 high risk, and ~30 low risk.

In analyzing the 2-year PFS rate, 90% exact binomial confidence intervals will be computed for each arm. Only eligible patients with confirmed P16+ status who started radiotherapy will be analyzed (by arm). The regimen will be considered worthy of further study if the higher limit of the computed 90% CI exceeds 85%.

Comparisons of 2-year PFS rates between Arms B and C, Arms B and D, and Arms C and D are exploratory endpoints. Since one of the randomized arms proposed in this study is likely to be selected for a follow-up phase III study, the exploratory comparison of 2-year PFS rate between the two randomized arms is more important and a p-value  $\leq 0.05$  will be considered statistically significant. For the other two comparisons (Arms B and D; Arms C and D), the Type I error rate of 5% will be divided by the two tests (i.e., 0.05/2 considered statistically significant). Therefore, the family-wise error rate of 0.10 will be protected for the multiple comparisons in the 2-year PFS rate among arms. Power for various differences in the 2-year PFS rate is shown below, assuming a two-sided Fisher's exact test and 90 analyzable patients in Arms B or C, and 120 analyzable patients in arm D.

Difference in 2-year PFS rate between arms	Arm C vs. Arm B	Arm B (or C) vs. Arm D
10% (85% vs. 75%)	0.32	0.27
15% (85% vs. 70%)	0.62	0.58
20% (85% vs. 65%)	0.85	0.83
25% (85% vs. 60%)	0.96	0.96

*Interim Analysis—1-year PFS rate*

To safeguard against an unacceptably high failure rate for Arm B and Arm C, in which both the radiation dose is reduced and chemotherapy is removed, an interim look at 1-year PFS rate will be performed for the first 40 eligible and treated patients in Arm B and Arm C, separately. It is expected, for either arm, 90% of patients will be alive and progression free at 1 year (Fakhry, C, JNCI, 2008). The event rate will be deemed too high if 6 or more such events are observed within 1 year, which corresponds to an empirical progression rate of 15%. In this case, the trial will be suspended and a panel review will be called. The following table summarizes the probability of suspending the trial under various true 1-year progression rates in Arm B (and Arm C). For instance, the probability of suspending the trial is at least 84% if the true 1-year progression rate is 20% or higher. The study will continue accrual while we are waiting for the decision from this interim analysis.

True 1-yr progression rate for patients with intermediate risk	0.10	0.15	0.20	0.25	0.30
Probability of suspending the trial	0.21	0.57	0.84	0.96	0.99

Similarly, to safeguard against an unacceptably high failure rate for the observational Arm A, an interim look at 1-year PFS rate will also be performed for the first 10 eligible and treated patients (a total of 38 patients is expected to be accrued to this arm). Among these 10 patients, if 2 or more patients progressed or died within 1 year, currently enrolled and subsequently enrolled low risk patients who have not progressed will be directly assigned to radiotherapy IMRT 50 Gy. The same interim monitoring rule will be applied to the patients with pathological N2C/N3 disease who are directly assigned to Arm C (expected to be 5% of the total population). That is, if 2 or more patients among the first 10 such patients progress or die within the first year, currently and subsequently enrolled patients with p N2C/N3 disease will be treated with IMRT 66 Gy + cisplatin (Arm D treatment). The following table summarizes the probability of observing 2 or more events, under various true 1-year PFS rate for this group of patients.

True 1-yr PFS rate	0.10	0.15	0.20	0.25	0.30
Probability of observing 2 or more events	0.26	0.46	0.62	0.76	0.85

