## 2. Objectives

### 2.1 Primary Objective

- 2.1.1 Accrual, risk distribution, and surgical quality will be used to determine the feasibility of a prospective multi-institutional study of transoral surgery for HPV+ oropharynx cancer followed by risk-adjusted adjuvant therapy.
- 2.1.2 To assess the oncologic efficacy following transoral resection and adjuvant therapy in patients determined to be at “intermediate risk” after surgical excision, the 2-year PFS rate will be examined.

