#### 5.1.8.4 Definition of Unknown-Risk Patient Cohort and Management: Arm C (5-7 weeks)

Patients found to have N2C or N3 disease on final pathologic analysis are at unknown risk for recurrence, but are not candidates for deintensified adjuvant therapy in this trial. These patients will be treated on Arm C.

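### The Arm C sets for the 2-year PFS rule and the first-40 rule do not exclude the pN2c/N3 patients assigned to Arm C without randomisation

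*Combined protocol and SAP*

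**What the plan says.** **Intended population.** Section 2.1 sets the efficacy aim: "To assess the oncologic efficacy following transoral resection and adjuvant therapy in patients determined to be at" intermediate risk. Section 9 calls the intermediate-risk patients, randomised equally to Arms B and C, the primary study group. Section 9.1 says the 2-year PFS "rate will be used to evaluate the efficacy in the intermediate risk group". Section 9.3 sizes on that basis: "Assuming 90 analyzable patients per arm for the intermediate group", and "This study will need 180 analyzable patients in total for the two randomized arms". The operating table for the first-40 rule is labelled for intermediate-risk patients.

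**Second route into Arm C.** Section 5.1.8.4 says that patients with pathological N2c or N3 disease "are at unknown risk for recurrence, but are not candidates for deintensified adjuvant therapy in this trial". Section 9 says that those without high-risk features "will be directly assigned to Arm C receiving IMRT 60 Gy". Section 9.3 expects them to be 5% of the total population and gives them their own first-10 rule.

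**Who is counted.** For the 2-year PFS rule, section 9.3 analyses only eligible patients with confirmed p16-positive "status who started radiotherapy will be analyzed (by arm"). Arm C passes if the upper limit of its exact 90% CI exceeds 85%. For the interim rule, the table in section 9.1 says "First 40 patients in each of arms" B and C, and section 9.3 says eligible and treated patients in each arm. Six or more events within a year suspend the trial for panel review. None of these sentences mentions randomisation or risk category.

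**The concern.** A pN2c/N3 patient who is eligible, p16-positive and irradiated satisfies every written condition for both Arm C sets, and nothing in the plan takes such a patient out. The first-10 rule is an additional rule and does not say that these patients leave the Arm C counts.

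Two formal decisions rest on these sets: whether the Arm C regimen is worthy of further study, and whether the trial is suspended. Someone programming from the set definitions alone would add a non-randomised group to Arm C and none to Arm B. The Arm C result would no longer describe the population for which the rules were sized. A suspension leads to panel review, where the mix might be noticed. The 2-year CI rule has no such step.

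**Working it through.** **Inputs from the plan.** 90 analysable patients per arm; about 376 evaluable of 515, with 180 intermediate risk; pN2c/N3 expected at 5%; pass if the exact 90% upper limit exceeds 85%; suspend at 6 or more events in 40; expected 1-year PFS 90% (sections 9.1 to 9.3).

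**Reproducing the plan.** P(at least 6 of 40) at event rates 0.10, 0.15, 0.20, 0.25 and 0.30 is 0.206, 0.568, 0.839, 0.957 and 0.991, matching the printed 0.21, 0.57, 0.84, 0.96 and 0.99. The exact 90% CI for 71 of 90 is (0.706, 0.857), matching (0.71, 0.86). Also 376 × 0.48 = 180, so the 180 is the intermediate-risk share alone and leaves no room for pN2c/N3 patients.

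**How many could be pooled.** 0.05 × 376 = 18.8, about 19; 19/(90 + 19) = 17.4%. If the first-10 rule triggers early and only those ten stay in Arm C, the share is 10/100 = 10%.

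**2-year PFS rule.** Progression-free count = Bin(90, 0.85) + Bin(m, q), where m is the number pooled and q their assumed 2-year PFS. The minimum count to pass is 71 of 90, 79 of 100 or 86 of 109. Without pooling, P(pass) = 0.957.

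| q | P(pass), m = 10 | P(pass), m = 19 | Expected Arm C rate, m = 19 |
|---|---|---|---|
| 0.95 | 0.981 | 0.992 | 0.867 |
| 0.85 | 0.961 | 0.968 | 0.850 |
| 0.75 | 0.930 | 0.909 | 0.833 |
| 0.65 | 0.886 | 0.803 | 0.815 |

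**First-40 rule.** Events = Bin(40 − k, 0.10) + Bin(k, r), where k is the number of pN2c/N3 patients among the first 40 and r their assumed 1-year event rate. The documents do not give k, so three values are used:
- k = 7: the constant mix, 40 × 19/109 = 7.0.
- k = 5: assumes about 12 Arm C patients entered before the direct route existed. Section 9.4 implies 69 patients by 15 January 2015 (59 with surgical data and 10 without), and 69 × 0.35/2 = 12. Then 28 × 19/109 = 4.9.
- k = 3: assumes none among the first 25 per arm (104 × 0.48/2 = 25, from the interim distribution). Then 15 × 19/109 = 2.6.

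| r | k = 3 | k = 5 | k = 7 |
|---|---|---|---|
| 0.05 | 0.18 | 0.17 | 0.15 |
| 0.10 | 0.21 | 0.21 | 0.21 |
| 0.20 | 0.26 | 0.29 | 0.33 |
| 0.30 | 0.31 | 0.38 | 0.46 |

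The entries are P(suspend). The plan's own value is 0.21.

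**The case against.** The strongest reply is that the population is already fixed. Sections 2.1, 9, 9.1 and 9.3 all point to randomised intermediate-risk patients, so the sentence on eligibility, p16 status and radiotherapy can be read as exclusions applied to a population already named. The separate first-10 rule suggests a separate cohort, and pooling would put the same patients under two rules. This stands as evidence of intent. It does not close the gap, because the sentence that lists the restrictions omits this one.

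A second reply is that the numbers may be small. The interim distribution in section 9.3 is 8% low, 48% intermediate, 32% high and 12% potentially misclassified, which totals 100% with no pN2c/N3 category. The documents do not say whether such patients were absent or counted elsewhere. This also stands, and it is why the first-40 range starts at 3.

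A third reply is that harm requires worse pN2c/N3 outcomes, which no section reports. That is correct. At equal outcomes P(suspend) is unchanged and P(pass) barely moves.

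A reader might infer that the B versus C comparison and the B/C quality-of-life analysis also mix in directly assigned patients. The text points the other way. Section 9.3 describes B versus C as a comparison of the two randomised arms. The quality-of-life counts in section 9.5 of 72, 108 and 144 are 40%, 60% and 80% of 180. Confirming the set is enough there.

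**Conclusion.** The point holds as a gap in wording at two formal decision rules. The definitions of the analysed sets do not exclude a non-randomised group that the rest of the plan treats as separate. It deserves correction because one of the rules is the primary efficacy decision for Arm C.

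The size is uncertain in both directions. With randomised 2-year PFS at 85% and 19 patients pooled, P(pass) ranges from 0.80 (20 points worse) to 0.99 (10 points better), against 0.957 without pooling. With 3 to 7 such patients among the first 40 and a 10% randomised event rate, P(suspend) is 0.15-0.18 at a 5% event rate, 0.26-0.33 at 20% and 0.31-0.46 at 30%, against 0.21. The pN2c/N3 outcomes, the number pooled and their timing are all assumptions.

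A reader might go further and conclude that the sponsor plans to pool, that Arm C will look worse as a result, or that the printed operating characteristics are wrong. The documents support none of these. The stated intent is intermediate risk, the protocol calls the pN2c/N3 risk unknown, and the printed figures reproduce for the population they name. Arm B's own sets are unaffected.

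**What to change.** State in section 9.3 that the Arm B and Arm C sets for the 2-year PFS 90% CI rule, the first-40 rule and the B versus C comparison contain only randomised intermediate-risk patients. Carry the same restriction into the first-40 row of the table in section 9.1. Report pN2c/N3 patients as a separate cohort, in line with their own first-10 rule.

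The cost is wording only. Risk category is recorded as a classification factor at Step 2 (section 4.2.4.1), and sample size and conduct do not change.

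A separate and minor improvement is to stratify the exploratory B versus C comparison by the smoking factor used in randomisation (section 9.8), which is also recorded at Step 2. Under an assumed 15-point difference in PFS between smoking strata, simulated power at 85% versus 75% rises from 0.384 to 0.400 without continuity correction, or from 0.320 to 0.329 with it, a gain of about 1 to 2 points. Leaving the comparison unstratified causes no bias.
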